### 9.2 Tests of Hypotheses and Significance Levels

The primary objective of the study is to compare the efficacy of defibrotide prophylaxis in addition to BSC (DP arm) vs BSC alone (BSC arm) for the prevention of hepatic VOD as measured by VOD-free survival by Day +30 in patients undergoing HSCT who are at high risk or very high risk for developing VOD by Day +30 post-HSCT. The study is designed with both an interim and a final analysis. To maintain an overall significance level at 1-sided alpha of 0.025, the incremental alpha is specified at 1-sided 0.0005 for interim analysis and 1-sided 0.0245 for final analysis (the corresponding nominal alpha is 1-sided 0.0005 for interim analysis and 1-sided 0.02498 for final analysis).

The key secondary objective of the study is to compare the efficacy of defibrotide prophylaxis in addition to BSC (DP arm) vs BSC alone (BSC arm) for the prevention of VOD as measured by VOD-free survival by Day +100 post-HSCT in patients who are at high risk or very high risk for developing VOD. To control the study-wise type I error, a sequential testing strategy will begin with the test on primary efficacy endpoint. If the test is significant, the test on the key secondary efficacy endpoint will be conducted at 1-sided alpha = 0.025. This gate-keeping approach will keep the family-wise error rate at 1-sided 0.025 for the comparisons of the 2 treatment arm in the primary and the key secondary efficacy endpoints.

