### 9.8.2 Key Secondary Efficacy Endpoint and Analysis

The key secondary efficacy endpoint is VOD-free survival by Day +100 post-HSCT and will be analyzed similarly to the primary efficacy endpoint.

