3 PURPOSE

This Statistical Analysis Plan (SAP) provides a detailed and complete description of the planned statistical analyses for the final analysis of Study 15-007 to support the Clinical Study Report (CSR). Mock tables, listings, and figures shells will be provided in a separate supporting document.

This SAP complies with the International Council for Harmonisation (ICH) Harmonised Tripartite Guideline Topic E9, Statistical Principles for Clinical Trials. The current version is based on Protocol version 4.0 dated 20 August 2018.

Biomarker and immunogenicity analysis plans and results will be provided in separate documents.

All decisions regarding the final analysis of the study results, as defined in this SAP document, will be made prior to database freeze of the study data.

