4.3.2.2 Key Secondary Study Hypothesis

The key secondary efficacy endpoint is a time-to-event endpoint. The statistical hypothesis is as follows:

- Null hypothesis (H_0): There is no difference in VOD-free survival by Day +100 post-HSCT between the DP and the BSC arms.
- Alternative hypothesis (H_1): There is a difference in VOD-free survival by Day +100 post-HSCT in favor of DP arm over BSC arm.

Superiority will be assessed using data from the ITT analysis set. To control the study-wise type I error, a sequential testing strategy will begin with the test on primary efficacy endpoint. If that test is significant, the test on the key secondary efficacy endpoint will be conducted at 1-sided alpha = 0.025. This gate-keeping approach will keep the family-wise error rate at 1-sided 0.025 for the comparisons of the 2 treatment arms in the primary and the key secondary efficacy endpoint analyses.

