7.2 Multiple Comparisons and Multiplicity

The primary objective of the study is to compare the efficacy of DP in addition to BSC (DP arm) vs BSC alone (BSC arm) for the prevention of VOD as measured by VOD-free survival by Day +30 post-HSCT in subjects who are at high risk or very high risk for developing VOD. The study is designed with both an interim and a final analysis. To maintain an overall significance level at 1-sided alpha of 0.025, the incremental alpha is specified at 1-sided 0.0005 for interim analysis and 1-sided 0.0245 for final analysis (the corresponding nominal alpha is 1-sided 0.0005 for interim analysis and 1-sided 0.02498 for final analysis).

The key secondary objective of the study is to compare the efficacy of DP in addition to BSC (DP arm) vs BSC alone (BSC arm) for the prevention of VOD as measured by VOD-free survival by Day +100 post-HSCT in subjects who are at high risk or very high risk for developing VOD. To control the study-wise type I error, a sequential testing strategy will begin with the test on primary efficacy endpoint. If the test is significant, the test on the key secondary efficacy endpoint will be conducted at 1-sided alpha = 0.025. This gate-keeping approach will keep the family-wise error rate at 1-sided 0.025 for the comparisons of the 2 treatment arms in the primary and the key secondary efficacy endpoint analyses.

Other endpoints including secondary efficacy endpoints will be tested without multiplicity adjustments, and nominal p-values will be reported.

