Similarly, the variance of the score is given by the sum of the variances calculated separately within each stratum:

$$V_1 = \sum_{s=1}^S V_s$$

$$\text{where } V_s = \sum_{j=1}^J \frac{r_{CSj} r_{ESj} d_{sj} (r_{sj} - d_{sj})}{r_{sj}^2 (r_{sj} - 1)}$$

The stage 2 stratified log rank statistic $Z_2 = U_2 / \sqrt{V_2}$ is calculated based on log rank score U_2 with variance V_2 .

Under the null hypothesis of no difference in survival curves within each stratum, Z_1 and Z_2 have standard normal asymptotic distribution. Thus, at the interim analysis the p-value is calculated as follows:

$$p_1 = 1 - \Phi(Z_1)$$

Let c_1 and c_2 be the efficacy boundaries at the interim and final analysis times such that

$$1 - \Phi(c_1) = 0.0005$$

or equivalently,

$$c_1 = \Phi^{-1}(0.9995) = 3.2905$$

And

$$P_0(Z_1 \leq c_1 \text{ and } Z_{CHW} > c_2) = 0.0245$$

Using numerical integration one can solve this equation to get $c_2 = 1.9603$.

Let

$$\alpha_2 = 1 - \Phi(c_2) = 0.02498$$

The decision rule for declaring efficacy at the interim analysis is as follows:

If $p_1 < 0.0005$, or equivalently $Z_1 > c_1$, then reject H_0 at the interim analysis and recommend stopping the trial early for overwhelming efficacy.

The p-value at the final analysis is defined by

$$p_{CHW} = 1 - \Phi(Z_{CHW})$$

The decision rule for declaring efficacy at the final analysis is:

If $p_{CHW} < \alpha_2$ or equivalently $Z_{CHW} > c_2$, then reject H_0 and declare efficacy.

Cui, Hung, and Wang have shown that the type-1 error will be preserved at the specified α level despite the possibility of a data dependent increase in the sample size.

The primary analysis will be performed on the ITT Analysis Set as described above. The independent stratified log rank statistics from stage 1 (Z_1) and stage 2 (Z_2) will be presented along with Z_{CHW} and the p-value (P_{CHW}). In addition, the following descriptive statistics will be presented to support the analysis of the primary efficacy endpoint:

- The number of subjects by treatment group who had an event and who were censored (either due to not having an event or for other reasons as described above).
- The Kaplan-Meier (KM) estimates of the VOD-free survival rate (%) by Day +30 post-HSCT (95% CI).
- the KM estimate of median time to VOD or death in days (95% CI).
- The HR (95% CI) from a Cox proportional hazards regression model stratified by risk status and age group.

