10.2 Analysis of Secondary Endpoints

10.2.1 Key Secondary Efficacy Endpoint

The key secondary efficacy endpoint is VOD-free survival by Day +100 post-HSCT and will be analyzed using the same methods described in Section [10.1](#) for the primary efficacy endpoint in the ITT Analysis Set.

The following summary will be provided:

- Analysis of VOD-free survival by Day +100 post-HSCT

The following figure will be provided:

- Figure of VOD-free survival by Day +100 post-HSCT

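### The SAP says a flat 1-sided 0.025 for the key secondary keeps the family-wise error at 0.025; with two looks at the primary this needs a stated level per look (about 0.027 on the literal reading; minor)

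*SAP*

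**What the plan says.** SAP 7.2 splits alpha by look for the primary only: incremental 0.0005 at the interim and 0.0245 at the final analysis (nominal 0.0005 and 0.02498), for 0.025 overall. For the key secondary, SAP 4.3.2.2 gives one level and names no look: if the primary is significant, "the test on the key secondary efficacy endpoint will be conducted at 1-sided alpha = 0.025". SAP 7.2 then concludes: "This gate-keeping approach will keep the family-wise error rate at 1-sided 0.025 for the comparisons of the 2 treatment arms". Protocol 9.2 says the same ("This gate-keeping approach will keep the family-wise error rate at 1-sided 0.025 for the comparisons of the 2 treatment arm"), as does the protocol synopsis.

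The primary can succeed at either look. SAP 10.1 rejects at the interim if Z1 exceeds 3.2905, in its words "at the interim analysis and recommend stopping the trial early for overwhelming efficacy"; otherwise the final criterion is Z_CHW > 1.9603.

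Three other places bear on how to read the flat 0.025:
- SAP 10.2.1 says the key secondary "will be analyzed using the same methods described in Section" 10.1. Protocol 9.8.2 says it "will be analyzed similarly to the primary efficacy endpoint".
- SAP 10.1 derives the distribution of the test statistics "Under the null hypothesis of no difference in survival curves within each stratum".
- SAP 3 limits this SAP to the "planned statistical analyses for the final analysis of Study 15-007". SAP 4.7 places the interim content and decision rules in a separate interim SAP (iSAP) and the DMC charter.

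**The concern.** Fixed-sequence testing controls the family-wise error when each hypothesis gets one test at the full level. Here the gate can open at either of two looks. If the secondary is then tested at 0.025 at whichever look opens it, one null hypothesis can be rejected at the full level on two different data sets. Splitting alpha for the primary does not protect the secondary when the primary null is false and the secondary null is true.

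At stake is the only claim besides the primary that is under alpha control. After an interim efficacy stop the text supports two critical values for Day +100: 1.96 (flat 0.025) or 3.29 (the Section 10.1 interim boundary). That choice should not be left until results are known.

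**Working it through.** **1. The plan's own figures.** With w = 252/360 = 0.7 and c1 = Φ⁻¹(0.9995) = 3.2905, solving P(Z1 ≤ c1, Z_CHW > c2) = 0.0245 gives c2 = 1.9603 and a nominal level of 0.02498. This matches SAP 10.1. The planned hazard ratio also matches: ln 0.86 / ln 0.72 = 0.459.

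**2. Error of the literal rule.** Let Y1 be the Day +100 statistic tested after an interim success and Y_F the one tested at the final analysis, both with zero drift:

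error = P(Z1 > 3.2905, Y1 > 1.96) + P(Z1 ≤ 3.2905, Z_CHW > 1.9603, Y_F > 1.96).

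Inputs from the documents are the boundaries, w, and 90% power at 1-sided 0.025, which gives a primary drift of 1.960 + 1.282 = 3.242. The interim stop probability is then 1 − Φ(3.2905 − √0.7 × 3.242) = 0.28. The documents give neither the correlation between the Day +30 and Day +100 statistics nor the secondary's information when it is tested, so both are assumed. Results from 6 million draws of jointly normal stagewise statistics (standard error about 0.00006):

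| Correlation | Interim term | Final term | Error, 0.7 information | Error, full information |
|---|---|---|---|---|
| 0.5 | 0.0187 | 0.0083 | 0.0270 | 0.0249 |
| 0.7 | 0.0230 | 0.0043 | 0.0273 | 0.0250 |
| 0.8 | 0.0244 | 0.0026 | 0.0270 | 0.0250 |
| 0.9 | 0.0250 | 0.0012 | 0.0261 | 0.0251 |

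At full information Y1 and Y_F are the same statistic, so the error cannot exceed P(Y_F > 1.96) = 0.025; the 0.0251 is simulation noise.

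**3. Other effect sizes.** Smaller Day +30 effects give more. Maximised over effect size at 0.7 information, the error is about 0.030 at correlation 0.82 and about 0.035 at 0.99. Under the literal rule with 0.7 information it cannot exceed P(Y1 > 1.96 or Y_F > 1.96) = 0.0378. At correlation 0.82 the maximum falls as information grows: 0.0297, 0.0277, 0.0262 and 0.0250 at 0.7, 0.8, 0.9 and 1.0.

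**4. What the null requires.** A patient-level simulation kept Day +30 events nested in Day +100 events (126 + 54 patients per arm, no censoring). Late events on defibrotide prophylaxis (DP) were set so that the Day +100 log-rank drift is zero. It gave 0.0269 to 0.0270 at 28% vs 14%, with correlation 0.77 to 0.82. With 2%, 4% or 6% late BSC events (assumed), 18.5%, 20.6% or 22.8% of DP patients must have a first event after Day +30, a late hazard ratio of about 8.6, 4.8 or 3.5 against DP. Day +100 event rates are then 30%, 32% or 34% on BSC and 14 + 18.5 = 32.5%, 34.6% or 36.8% on DP. At 28% vs 18% the error was 0.0301 to 0.0307, with late hazard ratios of 2.9 to 6.5 and a stop probability of 8%.

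**5. A split level restores control.** Using 0.0005/0.02498 for the secondary, P(Y1 > 3.2905) + P(Y1 ≤ 3.2905, Y_F > 1.9603) = 0.0005 + 0.0245 = 0.025, whatever the primary effect. At the planned drift the actual error is 0.0087, 0.0048, 0.0030 and 0.0016 for the four correlations. Another valid pair is about 0.0162 at each look (Z > 2.139 at 0.7 information).

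**The case against.** The strongest reply is that the claim is true under the null that the SAP uses. SAP 10.1 defines the log-rank null as identical curves, and SAP 10.2.1 applies the same methods to Day +100. Curves identical to Day +100 are identical to Day +30, so the primary null also holds and the gate itself caps the error at 0.025. In the counterexample the arms do differ: early and late log-rank contributions cancel, and DP ends slightly worse at Day +100. Nothing in the documents suggests such a reversal, and Protocol 1.4 describes VOD cases as late as Day +65 as infrequent. This stands as a limit on likelihood. It does not settle the text: SAP 4.3.2.2 states the Day +100 null separately, without saying that it means identical curves from the start.

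The second reply is that the shared methods carry over the Section 10.1 boundaries, so 0.025 is already an overall level. That is plausible, but it sits awkwardly with two sections that say the secondary test itself is run at 0.025, when the carried-over final level would be 0.02498.

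Third, the excess arises only after an interim stop, and the interim rules are in the iSAP. If the trial reaches its final analysis, the secondary is tested once and is bounded by 0.025. This also stands: that no level by look is stated can be said only of the protocol and this SAP.

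A reader might infer more than the documents support:
- *The trial's type I error is inflated.* The primary's boundaries reproduce exactly and are unaffected, and two reasonable readings control the secondary.
- *A secondary that fails at the interim is tested again at the final analysis* (0.035 to 0.038 at planned rates for correlation 0.5 to 1). Nothing in the text provides for this.
- *About 0.030 is the worst case.* It is the maximum at correlation 0.82 only.
- *0.0005/0.02498 is the only valid split.* Any pair spending 0.025 in total works.

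**Conclusion.** The concern holds as a minor clarification. The unconditional statement that the family-wise error stays at 0.025 is not a property of the rule as literally written. At the planned rates the excess is about 0.002 (error about 0.027), resting on assumed correlation 0.5 to 0.8 and about 70% secondary information at an interim stop. It grows for smaller Day +30 effects, and disappears at full information or under either alternative reading. The scenario also needs a late reversal against DP. What matters in practice is less the 0.002 than the open choice between 1.96 and 3.29 after an early stop. Confidence is medium, because the iSAP may already answer the question.

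**What to change.** In SAP 7.2, 4.3.2.2 and 10.2.1, state that 0.025 is the overall level for the key secondary across the two looks. Before comparative results are known, name the level at each look and say when Day +100 is tested after an early stop. The primary's 0.0005/0.02498 is the simplest choice and fits SAP 10.2.1. Any split spending 0.025 in total is acceptable, as is a single test at full planned information. If the iSAP already fixes this, cite it in SAP 7.2 instead.

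The cost is wording in three SAP sections. Protocol 9.2 and the synopsis require a formal amendment with IRB/IEC approval (Protocol 11.6), so they can be aligned at the next one. The statistical price of a split is a stricter Day +100 test after an early stop: 3.29 instead of 1.96 under 0.0005/0.02498, or about 2.14 under an equal split. At the final analysis 0.0005/0.02498 moves the critical value only from 1.9600 to 1.9603, whereas the equal split would raise it to about 2.14.

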8 DATA HANDLING CONVENTIONS

8.1 Missing Data

8.1.1 Imputation of Non-Date Missing Data

Missing data occurs when any requested data is not provided, leading to blank fields on the collection instrument. These data will be indicated by the use of a "blank" in subject listing displays. Note that if any missing data is imputed, the imputed data will only be used in

summaries, and will not be included in any listing. Answers such as “Not applicable” and “Not evaluable” are not considered to be missing data and should not be displayed as missing.

Subjects with the designation of treatment relationship for AEs and SAEs missing will have the worst case assumed to impute the relationship: if relationship to study treatment is missing it will be assumed to be “Yes”. There will be no other imputation for missing data other than as described in Section [8.1.2](#) for partial dates and times.

8.1.2 Imputation of Partial Dates

8.1.2.1 Incomplete and Missing Adverse Event Start Date

The following imputation rules will be followed, when the AE start date is incomplete (eg, only *year* is present, but *month* and *day* are missing) or completely missing:

- If *year* is missing (including the situation where the start date is completely missing), set the date to the first dose date.
- If *year* is present, and *month* and *day* are missing, or *year* and *day* are present, and *month* is missing,
 - if *year* = year of first dose, set the date to the first dose date;
 - if *year* < year of first dose, set *month* and *day* to December 31st;
 - if *year* > year of first dose, set *month* and *day* to January 1st.
- If *year* and *month* are present, and *day* is missing,
 - if *year* = year of first dose, and
 - if *month* = month of first dose, set *day* to day of first dose;
 - if *month* < month of first dose, set *day* to the last day of *month*;
 - if *month* > month of first dose, set *day* to the first day of *month*;
 - if *year* < year of first dose, set *day* to the last day of *month*;
 - if *year* > year of first dose, set *day* to the first day of *month*.
- For all other cases that are not covered above, set the date to the first dose date.

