#### **6.8.1.5 Adverse Event Recording and Reporting**

At a minimum, for patients in either the DP or BSC arm, the investigator must record all AEs and SAEs that occur from the time written informed consent is obtained until Day +60 post-HSCT (or screen failure), regardless of their relationship to study drug or procedure.

Even if the minimum of Day +60 post-HSCT is met, the investigator must continue to record all AEs and SAEs that occur within 30 days after the last dose of defibrotide, regardless of their relationship to study drug or procedure.

For patients who do not receive HSCT, AEs must be collected for 70 days after baseline or early termination, whichever occurs first. For patients randomized but not treated, AEs will be collected for 70 days after randomization or early termination, whichever occurs first.

Any SAE assessed as related to defibrotide or study procedures by the investigator, regardless of time after study termination, must also be recorded.

SAEs must be reported to the Sponsor or its designee using the SAE Reporting Form within 24 hours of first knowledge of the event by study site personnel. Serious adverse event Reporting Forms and contact information will be provided to the study sites separately.

The SAE Reporting Form must be completed as thoroughly as possible before transmittal to the contact provided on the form. The investigator must provide his/her assessment of causality to the study drug and the study procedure at the time of the initial report. If the investigator does not provide a causality assessment of the SAE at the time of the initial report, the event by default will be presumed to be “related”. Follow-up SAE information must be provided to the Sponsor if there are any updates to SAE information previously provided.

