11.2 Adverse Events

Adverse events recorded in the case report form will be coded to SOC and PT using the MedDRA 19.1. The investigator will assess the relatedness of each AE to study drug. The severity of AEs will be recorded using the Common Terminology Criteria for Adverse Events (CTCAE 4.03).

At a minimum, for subjects in either the DP or BSC arm, the investigator must record all AEs and SAEs that occur from the time written informed consent is obtained until screen failure if applicable, or Day +60 post-HSCT, regardless of their relationship to study drug or procedure. Even if the minimum of Day +60 post-HSCT is met, the investigator must continue to record all AEs and SAEs that occur within 30 days after the last dose of defibrotide, regardless of their relationship to study drug or procedure. For subjects who do not receive HSCT, AEs must be collected for 70 days after Baseline or early termination, whichever occurs first. For subjects randomized but not treated, AEs will be collected for 70 days after randomization or early termination, whichever is earlier. Any SAE assessed as related to defibrotide or study procedures by the investigator should be reported regardless of time after study termination. Related SAEs reported after study termination will be collected in the Safety database only.

A treatment-emergent adverse event (TEAE) is defined as any event with onset date on or after the first dose of study treatment (either DP or conditioning regimen) or any ongoing event that worsens in severity after the date of the first dose of study treatment through the protocol-specific reporting period. Only TEAEs with the onset date on or before the end of the protocol-specific AE reporting period noted above will be included in summary tables unless otherwise specified. All AEs will be listed. For the purpose of calculating treatment emergence, incomplete onset dates will be imputed as detailed in Section [8.1.2.1](#).

AEs are graded by the investigator as Grade 1 (mild), Grade 2 (moderate), Grade 3 (severe), Grade 4 (life threatening), or Grade 5 (fatal). The severity grade of events for which the investigator did not record severity will be categorized as “missing” for tabular summaries and data listings, and will be considered the least severe for the purposes of sorting for data presentation.

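### The AE start-date imputation never consults the AE stop date, so an event that ended before first dose can be flagged treatment-emergent

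*SAP*

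**What the plan says.** SAP 8.1.2.1 has four routes by which an incomplete AE start date becomes the first-dose date:

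- Year unknown, or no date at all: "including the situation where the start date is completely missing), set the date to the first dose date".
- Month unknown, year equal to that of first dose: "year of first dose, set the date to the first dose date".
- Only the day unknown, year and month equal to those of first dose: "if *month* = month of first dose, set *day* to day of first dose".
- Anything left over: "For all other cases that are not covered above, set the date to the first dose date".

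A known earlier month or year is imputed to the end of that period, and a known later one to its beginning. No line mentions the stop date. SAP 8.1.1 excludes any rule elsewhere: "There will be no other imputation for missing data other than as described in Section" 8.1.2.

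SAP 11.2 decides by onset date which records count as treatment-emergent (TEAEs). The wording there is that a TEAE of this kind "is defined as any event with onset date on or after the first dose of study treatment (either DP or conditioning regimen"). Also counted is a continuing event that becomes more severe once treatment has begun. The link to the date rules is explicit: "For the purpose of calculating treatment emergence, incomplete onset dates will be imputed as detailed in Section" 8.1.2.1. No exclusion is made for events that ended earlier.

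Protocol 6.8.1.5 has investigators record "all AEs and SAEs that occur from the time written informed consent is obtained", so pre-dose events are in the database. Stop dates are held too: SAP 11.2 lists the end date of each AE, and Protocol 9.14.1 lists the stop date where available.

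**The concern.** Assigning an unknown onset to the first-dose date is a sensible cautious convention when the timing really is unknown. It is not sensible when a reported stop date already shows that the event was over before treatment began. Followed exactly, the rule then overrides known information. It gives the event an onset later than its own end and passes it to the TEAE test, which it meets.

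The Prophylaxis Phase starts on the Baseline date, which is the earlier of first defibrotide and first conditioning (SAP 8.2.1 and 8.3). The misplaced event therefore falls on the first day of that phase and can enter its TEAE, Grade 3 or 4 and special-interest summaries. The SAP does use end dates when it sorts medications into prior and concomitant (8.1.2.3 and 9.5), but AEs get no equivalent step.

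**Working it through.** The documents give no figure to reproduce. The check applies the 8.1.2.1 rules and the 11.2 onset criterion as written.

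**Example.** First dose 15 March 2019, reported AE stop 10 March 2019:

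| Known part of start date | Imputed onset | TEAE? |
|---|---|---|
| nothing | 15 March | yes |
| 2019 | 15 March | yes |
| March 2019 | 15 March | yes |
| February 2019 | 28 February | no |

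In the first three rows the onset is 5 days after the event ended.

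**Conditional shares.** Inputs: a pre-dose window of days -14 to -1, from the screening period in Protocol 7.1.1. Assumptions: every first-dose date in 2019, and every onset and stop pair inside the window, equally weighted. An onset *a* days before first dose (*a* = 1 to 14) can be paired with *a* stop days.

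- Pairs per first-dose date: 1 + 2 + ... + 14 = 105. Combinations: 365 × 105 = 38,325.
- *Start fully missing:* all go to the first-dose date. 38,325 / 38,325 = **100%**.
- *Month missing:* the event escapes only if its onset lies in the previous year. For onset *a* this occurs on *a* first-dose dates in January, each with *a* stop days, so the number escaping is the sum of *a*² = 14 × 15 × 29 / 6 = 1,015. Misflagged: (38,325 − 1,015) / 38,325 = 37,310 / 38,325 = **97.4%**.
- *Only the day missing:* the event escapes if its onset lies in an earlier month. The same count arises in each of 12 months: 12 × 1,015 = 12,180. Misflagged: (38,325 − 12,180) / 38,325 = 26,145 / 38,325 = **68.2%**.
- *Cross-check with 30-day months:* mean onset 1,015 / 105 = 9.67 days before first dose, so (30 − 9.67) / 30 = 67.8%.

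With only the day missing, 31,605 combinations receive an onset after their own stop. The 31,605 − 26,145 = 5,460 that are not TEAEs come from a known earlier month imputed to its last day. Their dates are out of order, but their classification is right.

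**With a stop-date check,** 0 of 38,325 combinations are TEAEs under every pattern.

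**The case against.** The other side has a good deal to say.

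- **The trigger is narrow.** The AE must arise after consent, end before first dose, have a usable stop date, and still lack a usable start date after cleaning. Protocol 10 and 11.8 provide programmed checks, manual review and on-site eCRF review. These make the case rarer. They do not name this check, so they do not exclude it.
- **The direction is cautious and the date rule is the same in both arms.** Treatment emergence is anchored to defibrotide or conditioning. This stands as a limit on harm, but it does not justify counting an event known to be pre-treatment.
- **Serious events are better protected.** They are reported within 24 hours (Protocol 6.8.1.5), and the two databases are reconciled before finalization (SAP 11.2). A reader might infer that the serious-event tables are distorted. The documents make that less likely, though not impossible.
- **Impossible dates will not be printed.** A reader might expect them in the output, but SAP 8.1.1 keeps imputed values out of listings. What a reader could see is a treatment-emergent flag beside an end date that precedes dosing.

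A reader might also infer a bias against defibrotide. The date rule itself gives no such bias. SAP 11.2 treats missing causality as related only in subjects who received defibrotide, so the consequence differs between arms only for an event missing both its causality and part of its start date.

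**Conclusion.** The rule, followed exactly, gives a wrong classification for an AE with an incomplete start date and a reported stop before first dose. It is a minor point. It concerns safety summaries only, over-counts TEAEs, and does not reach the primary or key secondary analysis.

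The number of affected events cannot be computed, because the documents give no count of partial dates; few are expected. The shares of about 68%, 97% and 100% apply only to AEs that both started and ended in days -14 to -1 and have the stated missing pattern. They rest on a uniform grid and are not expected trial rates. Protocol 7.1.2 allows conditioning to be postponed after randomization, so the real window can be longer than 14 days.

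A reader might average over all pre-dose onsets and obtain (30 − 7.5) / 30 = 75% for a missing day. That figure includes events still ongoing at first dose, which have no earlier stop date to contradict the imputation, so it does not measure this defect.

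**What to change.** Place one rule ahead of the others in SAP 8.1.2.1:

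- If the AE stop date, or the known part of a partial stop date, places the end of the event before first dose, the event is not treatment-emergent. Its imputed start may not be later than the stop date, or than the latest date consistent with a partial stop date.
- If the stop date is missing, the event is ongoing, the stop is on or after first dose, or the stop is too incomplete to place before first dose, the present rules apply.

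For a first dose on 15 March, a stop known only as February falls under the new rule, while a stop known only as March stays under the present ones. A worsening after first dose is not lost, because Protocol 6.8.1.2 records an increase in severity as a new AE with its own start.

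The cost is a short addition to the SAP, with a matching reference in 11.2, and one condition in the derivation program. SAP 3 requires such decisions before the database freeze.
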